In the case of an unanticipated adverse device effects (UADE), the overall study may be suspended while the problem is diagnosed and the PI investigates the UADE. If the PI determines that the UADE poses an unreasonable risk to subjects, the study should be suspended until this UADE can be resolved. If it cannot be resolved, the study should be terminated. Termination should occur no later than 5 working days after PI makes the decision. The result of the investigation and the PI's decision to terminate the study shall be reported the site IRB, and the FDA per 21CFR 812.46(b) (2). The medical monitor must determine if the UADE presents an unreasonable risk to subjects. If so, the medical monitor must ensure that all investigations, or parts of investigations presenting that risk, are terminated as soon as possible but no later than 5 working days after the medical monitor makes this determination and no later than 15 working days after first receipt notice of the UADE.

The study may resume if the underlying problem can be corrected by a protocol or system modification that will not invalidate the results obtained prior to suspension. The IRB will be notified if the study is stopped, and permission to resume will be obtained from the FDA and IRB prior to restarting.

SUBJECT WITHDRAWAL CRITERIA

An individual subject can be stopped from study participation at subject, PI, study MD, or sponsor's request.

The Principal Investigator, IRB-HSR, or Safety Officer may decide to stop the trial or part of the trial at any time. In this case, the Study MD will promptly inform the subject and assure appropriate therapy and follow-up. Additionally, the Principal Investigator will promptly inform the IRB and provide a detailed written explanation. The pertinent regulatory authorities will be informed according to national regulations.

The subject may request to be withdrawn from the study at any time for any/no reason. A subject will be withdrawn at the subject's request (withdrawal of informed consent) or at the request of the PI or sponsor.

Study procedures other than those required for subject safety would be stopped if:

- The subject had a serious adverse event deemed related to study.
- Glucagon is required to treat hypoglycemia.
- The subject experiences a hypoglycemic seizure.
- The subject becomes unconscious due to hypoglycemia.
- SMBG <45 mg/dL at any time during the experimental session

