- SMBG >300 mg/dL for more than 2 hours during the experimental session
- SMBG \geq 400 mg/dL at any time during the experimental session
- The subject develops emesis, nausea and abdominal pain during the experimental session.
- Confirmed β -ketone level \geq 0.6 mmol/L for more than 2 hours during the experimental session
- Confirmed β -ketone level >1.5 mmol/L at any time

- System is in 'Stopped Mode' for more than 2 consecutive hours during the experimental sessions
- The subject has a positive pregnancy test.

Subjects who were not able to complete the study for reasons other than a serious adverse event (i.e. hypoglycemic seizure, etc.) will be permitted to repeat the session.

Reason Study Stopped	Repeat Session?
Equipment Failure or similarly related issues that invalidate study data	Can repeat session
Hyperglycemic Events that did not result in Serious Adverse Event	Can repeat session
Hypoglycemic Events that did not result in Serious Adverse Event	Can repeat session
PI initiated discontinuation of study due to patient or equipment concerns	Can repeat session
Serious or unanticipated adverse event deemed related to the study	Unable to repeat session

Table 1: Repeat Session Table

CATASTROPHIC EVENT PLAN

The Outpatient Emergency Plan will go into effect should a catastrophic event occur during the experimental session. A catastrophic event is defined as any event that requires emergency treatment by medical professionals that exceed the expected parameters of the protocol. A copy of this plan will be located at the monitoring desk. Staff will be aware of its location at all times.

Event	RN Response	Tech Response
Respiratory Arrest	1) Tell Tech to call 911 2) Begin Basic Life Support	Refer to Study Physician on-site
Cardiac Arrest	1) Tell Tech to call 911 2) Begin Basic Life Support	Refer to Study Physician on-site
Severe Hypoglycemic Event as defined by hypoglycemia accompanied by unconsciousness or seizure	1) Tell Tech to call 911 2) Administer glucagon IM (described in Hypoglycemia Safety	Refer to Study Physician on-site
Severe Hyperglycemic Event as defined by β -ketone level ≥ 0.6 mmol/L for >2 hours or >1.5 mmol/L, or symptoms of vomiting or abdominal pain are present	1) Discuss correction dose of insulin to administer s.c. via syringe with study M.D. 2) Encourage p.o. water intake	Refer to Study Physician on-site

Table 2: Outpatient Emergency Plan

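### The symptom trigger in the mandatory session-stop list does not match the symptom leg of the Severe Hyperglycemic Event in Table 2, and no supplied text says whether such an event ends the session.

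*Combined protocol and SAP*

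**What the plan says.** Section I, Subject Withdrawal Criteria, introduces a list with "Study procedures other than those required for subject safety would be stopped if", and each bullet that follows is a separate trigger. The symptom bullet reads "The subject develops emesis, nausea and abdominal pain during the experimental session". Other bullets cover glucose, for example "SMBG >300 mg/dL for more than 2 hours during the experimental session", and ketones, for example "ketone level >1.5 mmol/L at any time". Ahead of the list the section also allows a discretionary stop: "An individual subject can be stopped from study participation at subject, PI, study MD, or sponsor's request".

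The Catastrophic Event Plan follows in the same section and covers the same session: "The Outpatient Emergency Plan will go into effect should a catastrophic event occur during the experimental session". Its Table 2 has a row for a Severe Hyperglycemic Event. That row is met by ketones at or above 0.6 mmol/L for over 2 hours, by ketones above 1.5 mmol/L, "or symptoms of vomiting or abdominal pain are present". The nurse's response begins "Discuss correction dose of insulin to administer s.c. via syringe with study M.D" and adds oral water. The technician's column points to the study physician. The row does not say whether the session stops or goes on.

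**The concern.** The two lists appear to describe the same clinical situation, since they share both ketone limits and the same session. On symptoms they part. One joins three symptoms with 'and'; the other joins two with 'or' and leaves nausea out. Staff holding both pages during a session could declare a severe event under one and find no matching stop criterion under the other. At stake is the clarity of a safety rule: whether an event that the plan itself calls severe ends the experimental session by rule or only if someone decides that it should.

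**Working it through.** No sample size, power or significance figure bears on this, so there is no plan figure to reproduce. The check sets the two lists side by side.

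**Leg by leg**

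| Leg | Stop list | Table 2, hyperglycemic row |
|---|---|---|
| Sustained ketones | ≥0.6 mmol/L for more than 2 hours, confirmed | ≥0.6 mmol/L for more than 2 hours |
| High ketones | >1.5 mmol/L, confirmed | >1.5 mmol/L |
| Symptoms | emesis, nausea and abdominal pain | vomiting or abdominal pain |
| Glucose | >300 mg/dL for more than 2 hours, or ≥400 mg/dL | no threshold given |

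The numerical ketone limits agree; the stop list adds only that the level be confirmed. In Table 2's severe hypoglycemia row, unconsciousness and seizure each have their own stop bullet. So of the clinical legs in the two glycemic rows, only the hyperglycemia symptom leg has no matching stop bullet.

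**Literal reading.** Let V be vomiting, N nausea and A abdominal pain. The stop bullet needs V and N and A. The Table 2 symptom leg needs V or A. Whenever the stop bullet is met, Table 2 is met too, but not the reverse. Vomiting without abdominal pain, for instance, meets Table 2 and not the stop bullet.

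**Does another bullet close the gap?** Sometimes. It stays open when all of these hold:
- SMBG is below 400 mg/dL and has not been above 300 mg/dL for more than 2 hours;
- confirmed ketones are not above 1.5 mmol/L and have not been at or above 0.6 mmol/L for more than 2 hours;
- no related serious adverse event has been declared and no other listed bullet applies.

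These conditions are compatible with hyperglycemia, so requiring it does not close the gap. No stop bullet refers to a Table 2 event. Within them, the only route to a stop is the discretionary one.

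**Loose reading.** Suppose 'and' in the stop bullet means any of the three. The stop bullet is then V or N or A, and every Table 2 symptom event is also a stop event. But nausea alone would stop the session without meeting Table 2. The lists differ under either reading, in opposite directions.

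**The case against.** The strongest reply is that the conjunctive reading is only assumed. The protocol does use 'and' loosely: exclusion criterion 17 joins a hematocrit below 30% to one above 55% in that way, and no subject can have both. Read so, the stop list is the wider of the two and the literal gap disappears. This stands as a possible reading, but it does not make the lists agree, because nausea alone then separates them.

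Second, Table 2 has a context. The row is headed as a hyperglycemic event, and the plan applies to events needing emergency professional treatment beyond what the protocol expects. It is arguable whether symptoms without hyperglycemia qualify. That narrows the gap without closing it, since the glucose stop bullets require a high level or a sustained one.

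Third, there are other safeguards: the glucose, ketone and serious-event bullets, the discretionary stop, Table 2's own referral to the study physician, and the medically qualified staff member present throughout. All of this stands. The gap is in the mandatory rule, not in the supervision of the subject.

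A reader might infer three stronger points that the documents do not support:
- *The two passages give opposite instructions.* They do not. Table 2 sets treatment and escalation and never says to continue; the stop list does not say to continue when its bullets are unmet. The triggers are inconsistent, but neither passage commands what the other forbids.
- *The number of symptom combinations on which the lists disagree measures the problem.* It does not. The documents give no frequencies, and equal weight for each combination would be arbitrary.
- *The mismatch decides which data enter the analysis.* Stopped sessions do bear on the repeat-session table and the 80% completion rule, but hyperglycemic stops without a serious adverse event may be repeated, and nothing in the documents lets an effect on the analysis be estimated.

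Finally, the Treatment Safety Protocols in Appendix A-6 are not in the supplied text. They may say what happens to closed-loop control in these circumstances, so it cannot be asserted that control would in fact continue.

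**Conclusion.** The mismatch is real and survives both readings of the stop bullet. Read literally, an event declared severe on vomiting or abdominal pain, short of all three stop symptoms, triggers no mandatory stop unless another bullet fires, and the decision falls to discretion, in practice that of the PI or study MD. Read loosely, the lists disagree on nausea alone.

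Its size is that of a narrow inconsistency in a safety trigger. It alters no stated statistical figure, and its frequency cannot be judged from the documents. It should be corrected because it concerns participant safety and is easily put right.

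The conclusion rests on two assumptions: that the stop list and the hyperglycemic row address the same clinical situation, which the shared ketone limits and common session suggest but the text does not state; and that Appendix A-6 does not already settle the matter. No view is taken on which symptom definition is clinically right.

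**What to change.** Reconcile the two passages in one of two ways. Either use a single symptom definition in the stop list and in Table 2, stating whether any or all of the symptoms are required; or state expressly that the two triggers differ, give the reason, and say whether a Table 2 event stops the session. The medical monitor and study physician should choose the wording and check it against the Appendix A-6 safety protocols so that all three places agree. The cost is about one line of protocol text, processed as an amendment; no design or analysis element changes.

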17. Care partners (e.g. spouse) can accompany study subject during the trial. The guest will be required to sign the Care Partner Consent Form.

Equipment Specifications:

1. All study equipment including the DiAs cell phone, computers, insulin pump, and CGM receivers will use atomic clocks as a reference.
2. The investigator or delegate determines which one of the two CGM units will be used in the DiAs System during the clinical trial, and documents the rationale for decision. For example, the most accurate CGM may be used, and may be determined by the closest sensor glucose value to the meter glucose value performed at the time. A problem with radiofrequency communication resulting in loss of sensor glucose values or other sensor problem may lead to the alternate CGM being used. If both CGM units are performing equally, either unit may be selected. If during the outpatient session, the selected CGM exhibits abnormalities, the alternate CGM will be used for the remainder of the visit. If the alternate CGM also exhibits abnormalities, the outpatient visit will be terminated and rescheduled.
3. DiAs will be initialized with the subject's insulin pump parameters and will be connected to the study pump. The study pump will be initiated, and the subject's home pump will be removed.
4. During the Experimental Admission, DiAs takes the place of the Aviva Combo device and assumes control of the pump via the same Bluetooth connection that the pump uses to communicate with the Aviva meter. The Aviva Combo device is unpaired with the pump and will be unable to communicate with the pump during the time when DiAs is active. The subject will use the One Touch Ultra 2 or the Aviva Combo glucometer for fingersticks only during the DiAs control of the insulin pump.
5. The subject will be trained to use the DiAs interface; the training will continue approximately an hour, or until all questions are answered – the DiAs User Manual is included in Appendix A-7.
6. The subject will be trained on DiAs and on how to respond to the AAA alerts. The study team will provide supervision during the session.
7. The subject will be primarily responsible for using the system at this time, with the study team serving as a back-up when needed. The subject will be re-educated as needed and will be provided printed reminders/instructions as a reference.
8. At approximately 19:00, the computer tech will initiate the closed-loop (AAA control) on DiAs.

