In the unlikely event of a disruption in 911 phone service, the Charlottesville-UVA-Albemarle Emergency Communications Center can be reached via their non-emergency number [contact]. This number feeds into their main call area where 911 dispatchers are available 24/7.

J. ENDPOINTS

This study is an early feasibility study that will test the efficacy of DiAs - a *smart-phone-based system* compared to CGM-enhanced insulin pump treatment in an outpatient setting. Specifically, the main study will have randomized cross-over design with each patient participating in two study weeks: 1) experimental involving 5 days of data collection followed by 2 days of AAA control using insulin pump and available CGM (however, treatment based on CGM will be discouraged) and 2) Control week involving 5 days of data collection followed by 2 structured days of study at home. This series of sessions will provide data for the regulatory approval of the AAA system and for its deployment in a longer-term trial of AAA at home. In addition, the data will be used to estimate the effect size of the AAA vs. CGM-enhanced insulin pump treatment in an outpatient setting.

The *basic unit for most analyses is the glucose trace of an individual*, i.e. a time-stamped series of CGM data recorded for each person. Summary characteristics and group-level analyses are derived after the individual traces are processed to produce meaningful individual markers of average glycemia and glucose variation. The following primary endpoints will be assessed:

- Risk for hypoglycemia as measured by the Low BG Index associated with exercise (SA1);
- Time spent within 70-180 mg/dl during the day (SA2);
- Risk for hypoglycemia overnight and time spent within the target range of 80-140 mg/dl overnight (SA3).

In addition, the following secondary endpoints will be assessed:

- Extent postprandial glucose excursions during the day;
- Overall number and extent of hypoglycemic episodes;
- System reliability, including failure rates of system components, frequency analysis of lost or inaccurate CGM records, percent time of active control, and inter-device connections between DiAs and the CGM and between DiAs and the insulin pump;
- System functionality, including the DiAs GUI in terms of patient comfort with operating the system, and
- The DiAs remote monitoring by medical personnel/technicians to confirm appropriate functioning outside of the hospital setting.

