The specific aim SA4 of the Substudy is exploratory – no significant results are expected, but we will assess the effect size of Control Modules 1+3 (SSM+BRM) preventing nocturnal hypoglycemia and increasing time within target (80-140mg/dl) overnight as compared to CGM-augmented pump alone.

K. SUCCESS CRITERIA / GOAL

We hypothesize that, compared to CGM-augmented insulin pump treatment, AAA control will result in moderate effect size of approximately 0.3-0.5 in terms of:

- Prevention of hypoglycemia during and following exercise more efficiently than state-of-the-art care based on CGM and insulin pump;
- Increased time within the target range of 70-180 mg/dl during the day;
- Prevention of nocturnal hypoglycemia and increase of the time within target range (80-140mg/dl) overnight.

As a general rule, a session will be considered useful for data analysis if the subject completes more than 80% of the active study protocol (29 out of 36 hours for the experimental session). Sessions completing less than 80% of the protocol will be rescheduled.

L. STATISTICAL ANALYSIS PLAN

The testing of the three specific aims of the main study involves different periods of time as presented in Figure 2. Thus, in addition to complete data, availability of partial data would allow testing some of the study hypotheses. Measures of time within target range, risk and occurrence of hypoglycemia, glucose variability and system stability will be computed as previously described and will be accompanied by appropriate plots [20]. Repeated measures ANOVA with contrasts will be used to compare the different study periods on the basis of these measures. Specifically:

- Comparing risk and occurrence of hypoglycemia during the 5-hour periods encompassing exercise (14:00-19:00) on open- vs. closed-loop control will address SA1;
- Comparing the time within target range (70-180mg/dl) during the day (7:00-23:00) on open- vs. advisory control will address SA2, and
- Comparing the time within target range (80-140mg/dl) and the risk for hypoglycemia overnight will address SA3 (see Figure 2).

II. INFORMED CONSENT

The Pilot Consent, the Informed Consent, and the Care Partner Consent are presented in Appendix A-8.

III. PATIENT CASE REPORT FORMS

Patient Case Report Forms are presented in Appendix A-9.

IV. INVESTIGATOR AGREEMENT FORMS

Investigators Agreements Forms are presented in Appendix A-10.

V. MONITORING INFORMATION

Data and Safety Monitoring Plan

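### The 80%-completion rule has no exception for the system-reliability endpoint, so applied literally it drops most session-ending system failures from the reliability figures

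*Combined protocol and SAP*

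**What the plan says.** Section I.J (Endpoints) names as a secondary endpoint "System reliability, including failure rates of system components, frequency analysis of lost or inaccurate CGM records, percent time of active control", together with the links between DiAs and the CGM and pump. It gives no session set and no denominator. Section I.L (Statistical Analysis Plan) says only that system stability will be computed by a previously described method, with a literature reference.

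The one rule on which sessions count appears in sections I.C and I.K: "As a general rule, a session will be considered useful for data analysis if the subject completes more than 80% of the active study protocol", glossed as "29 out of 36 hours for the experimental session". It continues: "Sessions completing less than 80% of the protocol will be rescheduled". No endpoint is exempted.

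Three provisions let the system itself end a session or cause it to be run again:

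- Section I.G.4, Equipment Specifications, on the two CGMs: "If the alternate CGM also exhibits abnormalities, the outpatient visit will be terminated and rescheduled".
- Section I.I, Subject Withdrawal Criteria: study procedures stop if the system is in Stopped Mode for more than 2 consecutive hours during the experimental session.
- Section I.I, Table 1: a session may be repeated after "Equipment Failure or similarly related issues that invalidate study data".

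Section I.I also says, of subjects who do not complete the protocol, that the data available will be used. Sections I.C and I.L say that partial data would permit some of the hypotheses to be tested. Neither statement mentions reliability.

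**The concern.** Completion of an experimental session depends partly on whether the equipment works. A rule that admits sessions by completion therefore selects on the outcome that the reliability endpoint is meant to measure. A session that ends at hour 10 because both CGMs failed has completed well under 80%. It is rescheduled, and under the general rule it is the repeat that counts.

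This matters because of the stated purpose of the data. Section I.J says: "This series of sessions will provide data for the regulatory approval of the AAA system", and adds that the sessions will support a longer trial at home. How often the system stops, and for what share of the intended time it is in control, are central questions for an early feasibility study. Figures restricted to sessions that ran nearly to the end would answer them too favourably.

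**Working it through.** **Reproducing the plan's figure.** Section I.B starts AAA control at 19:00 and ends it at 7:00 on day 3: 5 + 24 + 7 = 36 h. Then 0.80 × 36 = 28.8 h, rounded up to 29 h, and 29/36 = 80.6%. The threshold is correct.

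**Inputs for the illustration.** From the documents: 36 h scheduled, a 29 h threshold, 36 completing subjects. Assumed, because the documents give neither a failure rate nor failure timing:

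- a share f of started sessions is ended by system failure, with f = 5%, 10% or 20%;
- failure times are uniform over the 36 h;
- control is fully active until failure.

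**Formulas.** The share of failures late enough to be kept is k = (36 − 29)/36 = 7/36 = 19.4%. A kept failure has run on average (29 + 36)/2 = 32.5 h, which is 32.5/36 = 90.3% of schedule. Any failed session has run on average 50% of schedule.

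- Retained share of started sessions: R = (1 − f) + f·k
- Failure rate among retained sessions: f·k / R
- Active-control time, all started sessions: (1 − f) + 0.5·f
- Active-control time, retained sessions: [(1 − f) + f·k × 0.903] / R
- Starts needed for 36 retained sessions: 36 / R

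**Worked case, f = 10%.** f·k = 0.0194 and R = 0.900 + 0.0194 = 0.9194. Failure rate: 0.0194/0.9194 = 2.1%. Active time, all started: 0.900 + 0.050 = 95.0%. Active time, retained: (0.900 + 0.0194 × 0.903)/0.9194 = 99.8%. Starts: 36/0.9194 = 39.2, of which about 3.2 drop out.

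| f (true failure rate) | Failure rate, retained | Active time, all started | Active time, retained | Starts for 36 retained | Dropped |
|---|---|---|---|---|---|
| 5% | 1.0% | 97.5% | 99.9% | 37.5 | 1.5 |
| 10% | 2.1% | 95.0% | 99.8% | 39.2 | 3.2 |
| 20% | 4.6% | 90.0% | 99.6% | 42.9 | 6.9 |

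**Sensitivity to timing.** The understatement depends on k. At f = 10%, if half of the failures came after hour 29 (k = 0.5), the retained rate would be 0.05/(0.90 + 0.05) = 5.3%. If none did (k = 0), it would be 0%.

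**A related conflict.** Take a second-CGM failure at hour 33. The session has completed 33/36 = 91.7%, so section I.K counts it as useful. Section I.G.4 terminates and reschedules the visit without regard to elapsed time. One subject could then have two sessions that qualify, and no rule says which enters the efficacy analysis.

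**The case against.** A reader might infer that reliability will be computed only on sessions in which the system did not fail, so that the reported failure rate is zero whatever the device does. The documents do not support that, for four reasons.

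- They never say that reliability uses retained sessions only. The 80% rule is called a general rule and stands beside the efficacy aims. The CGM provision and Table 1 govern rescheduling and repeats; neither says that data from the first attempt are discarded. Table 1 is permissive and limited to failures that invalidate data.
- Section I.I says that available data from non-completers will be used.
- Much failure stays visible even under the rule: a first-CGM failure (the session continues on the alternate), Stopped Mode of up to 2 consecutive hours, lost records, dropped connections, and any stop after hour 29.
- The listed endpoint is the failure rate of components. A session-ending failure rate is not named separately.

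All of this stands against the stronger reading. It does not remove the point. The statement on available data names no endpoint, method or denominator, and the partial-data sentence concerns hypothesis tests. The reference behind system stability lies outside the plan, so whether it defines a session set cannot be checked here. Section V has the principal investigator review each subject's data for proper DiAs function, but that is oversight and not an analysis set. What remains is an inclusion rule with no exception for the one endpoint on whose outcome it selects.

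**Conclusion.** The concern holds as a selection problem that follows if the 80% rule is applied as written. It would remove most session-ending system failures, though not all failures. Under uniform timing the session-failure rate is understated four- to five-fold, and active-control time appears close to 100% across the whole assumed range. The direction follows from the rules: the dropped sessions are those with the earliest stops. The size rests on assumed failure rates, even timing and full control until failure, and the understatement shrinks if failures cluster late. The endpoint is secondary, and the power stated for SA1 to SA3 is not in question here. The change is worth making because reliability is a central feasibility result and the correction is cheap.

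**What to change.** In sections I.J and I.L:

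- State that the 80% rule does not apply to the reliability and functionality endpoints.
- Compute them on every experimental session in which AAA control was started, including terminated, rescheduled and repeated ones.
- Report failures per started session, and active-control time against scheduled control time.
- Show stops for equipment reasons separately from clinical or subject-initiated stops. Otherwise hours lost after, for example, a glucose- or ketone-based stop would count as device downtime.

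Sections I.G.4 and I.K must also be reconciled for a second-CGM failure after hour 29, and the plan should state which session enters the efficacy analysis when a subject has two. How such sessions are handled is for the sponsor to settle.

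The cost is a few sentences of plan text and slightly more analysis; section VII says the system already stores session data. The reliability figures may look less favourable. The reliability change leaves the primary endpoints untouched.
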